## **13 STATISTICAL CONSIDERATIONS**

### 13.1 Sample Size

A sample size of 31 subjects per group will have 90% power at a two-tailed significance level of 0.05 to detect a difference in the primary efficacy outcome EBV shedding of 70% in the treated group to 30% in the control group. With a dropout rate of approximately 30%, this study will require a total of 44 patients per group.

### Sample Size in Bronchoscopy sub study

The exploratory bronchoscopy sub-study will be voluntary for participants recruited to the EViSCO trial and thus no formal sample size calculation has been performed.

## 13.2 Data Analysis

Analyses will be on an intention-to-treat basis and all statistical tests will be at the 2sided p-value of 0.05.

Comparison between groups for the primary safety outcome measure, incidence of SARs will be carried out using Fisher's exact test.

The primary efficacy outcome, suppression of EBV shedding will initially be analysed using chi-square test. Logistic regression will be used for adjusting for covariates if required. The comparison of continuous secondary/exploratory outcomes will be initially by t-tests followed by analysis of covariance or any other appropriate methodology if required. Statistical diagnostic methods will be used to check for violations of the assumptions, and transformations will be performed where required.

Correlations between changes in the biological markers measured and physiological and clinical outcomes will be assessed by appropriate graphical and statistical methods including Pearson's (or Spearman's) correlation coefficient.

A single final analysis is planned at the end of the trial. A detailed statistical analysis Plan will be written prior to the final statistical analysis.

## **14 STUDY MONITORING**

## 14.1 Data Access

The agreement with the CI or designee will include permission for trial related monitoring, audits, ethics committee review and regulatory inspections, by providing direct access to source data and trial related documentation. Consent from patients and informants for direct access to data will also be obtained. The patients' confidentiality will be maintained and will not be made publicly available to the extent permitted by the applicable laws and regulations.

## **14.2 Monitoring Arrangements**

On-site monitoring visits will be undertaken by the CTU and conducted in accordance with the study-monitoring plan. On-site monitoring will be an ongoing activity from the time of initiation until study closeout and will comply with the principles of GCP and EU directive 2001/20/EC.

The frequency and type of monitoring will be detailed in the monitoring plan and agreed by the trial Sponsor.

Before the study starts a pre-initiation visit will take place to ensure that all relevant essential documents and trial supplies are in place and that site staff are fully aware of the study protocol and SOPs. During the study, on site monitoring visits will check the completeness of patient records, the accuracy of entries on CRFs, the adherence to the protocol, SOPs and GCP, and the progress of patient recruitment. Monitoring will also ensure that the study drug is being stored, dispensed and accounted for according to specifications. The CI or designee should ensure that access to all trial related documents including source documents (to confirm their consistency with CRF entries) are available during monitoring visits. The extent of source data verification (SDV) will be documented in the monitoring plan.

## **15 TRIAL COMMITTEES**

The Chief Investigator (CI) will have overall responsibility for the conduct of the study. The Northern Ireland Clinical Trials Unit (NICTU) will undertake data management, statistics and monitoring. The CI will be responsible on a day-to-day basis for overseeing and co-ordinating the work of the multi-disciplinary trial team and will be the main point of contact across the study team.

## 15.1 Trial Management Group (TMG)

Trial Management Group (TMG) will be established and chaired by the CI. The TMG will have representation on it from NICTU and other investigators or members of collaborating groups who are involved in the study and provide trial specific expertise. This group will have responsibility for the day-to-day operational management of the trial, and regular meetings of the TMG will be held to discuss and solve problems and monitor progress. The discussions of the TMG will be formally minuted and a record kept in the TMF.

## 15.2 Data Monitoring and Ethics Committee (DMEC)

A DMEC will be appointed with responsibility for safeguarding the interests of trial patients, they will monitor the main outcome measures including safety and efficacy so as to protect the validity and credibility of the trial. The committee members will be independent of the study team and will comprise of at least two respiratory specialists and one statistician. The DMEC Charter will outline the terms of reference of the DMEC including roles/responsibilities, membership, organisation of meetings, reporting, decision-making and the relationship with the other trial committees.

The DMEC will discuss trial progress as and when required, but at least every 9 months, meetings will be held and will be formally minuted. The Trial Statistician will produce reports for the DMEC including recruitment, baseline, adverse event, compliance and outcome data to enable them to monitor the trial and guide overall progress. An interim analysis of efficacy is not planned, although this can be requested by the DMEC as required.

The DMEC will function primarily as a check for safety reviewing adverse events (AEs). They will specifically review the incidence of ARs, SAEs and SUSARs and produce a recommendation following each meeting. They will report any issues pertaining to safety to both the study sponsor and the Chief Investigator. If concerns exist about participant safety it will be the responsibility of both to take appropriate action to halt the trial immediately.

#### 15.3 User Involvement

Patient and Public Involvement (PPI) will be integrated during the study through working closely with patients who attend the COPD patient meetings at the Mater Hospital.

## **16 REGULATIONS, ETHICS AND GOVERNANCE**

## 16.1 Sponsorship

The Belfast Health and Social Care Trust (BHSCT) will act as Sponsor for the study and the CI will take overall responsibility for the conduct of the trial. Separate agreements will be put in place between the Sponsor, CI and each organisation who will undertake delegated Sponsor duties in relation to the management of the study.

## **16.2 Regulatory and Ethical Approvals**

The trial will be conducted in accordance with the ethical principles that have their origin in the Declaration of Helsinki. The protocol will be approved by a Research Ethics Committee (REC). The trial will be conducted in accordance with the EU Directive 2001/20/EC and adhere to the appropriate regulatory requirements. A CTA will be obtained from the MHRA before the start of the trial. The trial will be registered with the International Standard Randomised Controlled Trial Number (ISRCTN) register and the European Union Drug Regulating Authorities Clinical Trials (EudraCT) database.

## **16.3 Good Clinical Practice**

The trial will be carried out in accordance with the principles of the International Conference on Harmonisation Good Clinical Practice (ICH-GCP) guidelines (www.ich.org). All members of the trial team will complete GCP training.

### **16.4 Protocol Compliance**

The CI or designee will conduct the study in compliance with the protocol given approval/favourable opinion by the Ethics Committee and the appropriate regulatory authority. Changes to the protocol may require competent authority/ethics committee approval/favourable opinion prior to implementation, except when modification is needed to eliminate an immediate hazard(s) to patients. The CI in collaboration with the sponsor will submit all protocol modifications to the competent authority/research ethics committees for review in accordance with the governing regulations. Protocol compliance will be monitored by the CTU who will undertake site visits to ensure that the trial protocol is adhered to and that necessary paperwork (e.g. CRF's, patient consent) is being completed appropriately. Any deviations from the protocol will be fully documented on the protocol deviation form in the CRF.

### **16.5 Patient Confidentiality**

Due care will be taken to ensure data safety, integrity and compliance with the Data Protection Act. The patient's trial identifier, name, address and other contact details of all patients will be kept separate. The CI or co-investigator will keep these details in a locked filing cabinet. All documentation regarding the study will identify the patients by the assigned unique trial identifier. Computers where information will be stored will be password protected. Patient confidentiality will be maintained at every stage and will not be made publicly available to the extent permitted by the applicable laws and regulations.

## **16.6 Record retention**

On completion of the trial the TMF and study data will be archived by the CI and CTU according to the applicable regulatory requirements and as required by the Sponsor.

### 16.7 Indemnity

The BHSCT will provide indemnity for any negligent harm caused to patients by the design of the research protocol and the management of the trial through the Clinical Negligence Fund in Northern Ireland.

#### 16.8 Finance

The study is funded by the YP Trustees, a charity associated with the Mater Hospital. [name] will manage the grant.

## 17 DISSEMINATION/PUBLICATIONS

The intention is to publish the results of this study in high quality peer-reviewed scientific journal(s). The TMG (and where appropriate collaborators) will take an active part in the preparing and reviewing of all manuscripts and reports generated during/on completion of the study. Any papers reporting the study outcome will be provided to collaborators and/or the Sponsors for advisory review and comment prior to submission for publication. The trial will be reported in accordance with the CONSORT guidelines (Schulz et al, 2010; www.consort-statement.org).

## **Definition of authorship**

An author is considered to be someone who has made substantive intellectual contribution to a study. Many journals consider it best practice that everyone who is listed as an author should have made a substantial, direct, intellectual contribution to the work. All investigators will potentially be co-authors and collaborators will be acknowledged. Honorary or guest authorship is not acceptable.

### **Dissemination Policy**

The trial will be reported in accordance with the Consolidated Standards of Reporting Trials (CONSORT) guidelines (www.consort-statement.org).

Dissemination will be achieved in several ways: (1) the findings will be presented at national and international meetings with open access abstracts on-line e.g. the American Thoracic Society annual meeting; and (2) in accordance with the open access policies proposed by the leading research funding bodies we aim to publish the findings in high quality peer-reviewed open access (via Pubmed) journals. This will secure a searchable compendium of these publications and make the results readily accessible to the public, health care professionals and scientists

At the end of the trial, all subjects will be written to thanking them for their participation in the study and provided with a short summary of the trial findings. Further details about the trial may be obtained on request.

---

**Appendix 1: Example Draft Summary Tables, FIGURES AND LISTINGS 27**

## ABBREVIATIONS

ABBREVIATION	DEFINITION
AE	Adverse Event
AR	Adverse Reaction
CAT	COPD Assessment Test
CI	Confidence Interval
COPD	Chronic Obstructive Pulmonary Disease
CRF	Case Report Form
CSR	Clinical Study Report
CTU	Clinical Trials Unit
EBV	Epstein-Barr Virus
EudraCT	European Clinical Trials Database
DMEC	Data Monitoring and Ethics Committee
DNA	Deoxyribonucleic Acid
EQ-5D-5L	EuroQol Quality of Life Questionnaire
FEV1	Forced Expiratory Volume in 1 Second
FVC	Forced Vital Capacity
GOLD	Global Initiative in Obstructive Lung Disease
ICAM-1	Intra Cellular Adhesion Marker 1
IL	Interleukin
ITT	Intention-To-Treat
NICTU	Northern Ireland Clinical Trials Unit
OR	Odds Ratio
PCR	Polymerase Chain Reaction
PP	Per-Protocol
RNA	Ribonucleic Acid
RSI	Reference Safety Information
SAE	Serious Adverse Event
SAP	Statistical Analysis Plan
SAR	Serious Adverse Reaction

SD	Standard Deviation
SOP	Standard Operating Procedures
SSAR	Suspected Serious Adverse Reaction
SUSAR	Suspected Unexpected Serious Adverse Reaction
TMF	Trial Master File
TSC	Trial Steering Committee
QoL	Quality of Life
UAR	Unexpected Adverse Reaction

# 1. BACKGROUND AND DESIGN

The primary hypothesis is that treatment with valaciclovir is safe and will suppress Epstein-Barr virus in the sputum of patients with COPD.

This study seeks to establish if an antiviral therapy (valaciclovir) used to treat other herpes viruses is safe in patients with COPD. It also examines whether it is possible to suppress Epstein-Barr virus (EBV) in the airways of patients with COPD and examine important outcome measures including lung function and markers of airway inflammation in the blood and sputum.

The EBV suppression in COPD (EViSCO) study will be a randomised double-blind placebo-controlled clinical trial. The EViSCO trial will recruit subjects with COPD (GOLD classification 2 and 3) and EBV detectable in their sputum samples. Trial participants will receive either valaciclovir one gram three times daily or a matching placebo for a total of 8 weeks. EViSCO trial participants will be recruited to the sub-study on a voluntary basis

## 1.1 Primary objective

- To evaluate the safety of valaciclovir (1 gram three times daily for 8 weeks) for the suppression of in patients with COPD.
- To suppress Epstein-Barr virus shedding in COPD..

## 1.2 Secondary objectives

- To determine the effect of EBV suppression on lung function (FEV1) in patients with COPD.
- To assess the tolerability of valaciclovir (1 gram three times daily for 8 weeks) by measuring participant compliance.

## 1.3 Exploratory objectives

- To measure the effect of EBV suppression on sputum and blood markers of inflammation in patients with COPD.

- To evaluate quality of life following EBV suppression in patients with COPD.

## 1.4 Inclusion and Exclusion Criteria

Patients will be eligible to participate in the study if they fulfil the following criteria:

### Inclusion Criteria

- 1) Age over 18 years.
- 2) Clinical diagnosis of COPD as defined by the Global Initiative for Chronic Obstructive Lung Disease criteria (FEV1/FVC <70%) with GOLD 2 and GOLD 3 airflow obstruction (FEV1 30-80% predicted) with significant symptoms.
- 3) Presence of EBV on sputum PCR analysis.

### Exclusion Criteria

- 1) Respiratory failure (defined as long-term oxygen therapy).
- 2) An acute exacerbation of COPD in the previous month (defined as an acute, sustained worsening of symptoms that is beyond normal day-to-day variations).
- 3) A diagnosis of asthma.
- 4) Patients with known hypersensitivity to valaciclovir or aciclovir.
- 5) Patients unable to swallow study drug capsules.
- 6) Established diffuse interstitial lung disease (e.g. Idiopathic Pulmonary Fibrosis).
- 7) Established diagnosis of symptomatic bronchiectasis\*.
- 8) Patients known to be pregnant or breastfeeding.
- 9) Patients with an estimated creatinine clearance less than 50ml/minute\*\*.
- 10) Known participation in investigational medicinal product trials within 30 days.
- 11) Patients who do not adequately understand verbal or written information.
- 12) Concomitant use of nephrotoxic medicinal products or medicines associated with altered renal tubular secretion. These include aminoglycosides, organoplatinum compounds, methotrexate, pentamidine, foscarnet, ciclosporin, tacrolimus, tenofovir, cimetidine and probenecid. As iodinated

[figure not shown]
contrast used in radiological examinations can be nephrotoxic any patients with planned radiological contrast studies will be deferred for a reasonable time until after their contrast.

- 13) For the exploratory bronchoscopy sub-study patients will require adequate oxygen saturations, FEV1 >0.5 L and will not be performed while patients are taking aspirin or clopidogrel (BTS guidelines 2013).

*\* Patients with a primary respiratory diagnosis of established symptomatic bronchiectasis will be excluded. In order to fulfil this exclusion criteria patients must exhibit the clinical bronchiectasis phenotype and demonstrate computed tomography (CT) evidence of established multi-lobar bronchiectasis.*

*\*\* Documented eGFR values from within the past 4 months will be used to confirm eligibility. If not available screening U&E will be completed.*

### 1.5 EViSCO Study Schematic Diagram

## 2. OUTCOME MEASURES

There are several study outcome measures:

### 2.1 Primary outcome measure(s)

- The primary safety outcome is the incidence of serious adverse reactions (SARs).
- The primary efficacy outcome is suppression of Epstein-Barr virus in the sputum of subjects with COPD and will be assessed using quantitative PCR at baseline and 8 weeks.

EBV is a DNA virus that may be suppressed beyond detection, however, it may be reverse transcribed and so it is possible that there will be some detectable virus. For this reason we will define EBV suppression as a 90% reduction in the viral load.

### 2.2 Secondary outcome measures

- Lung function measured by spirometry, the principal component will be the change in FEV1 from baseline to week 8\*.
- Participant compliance measured by total number of tablets administered as a proportion of total number of tablets supplied.

\* In light of the COVID19 lockdown lung function will not be measured in order to prevent unnecessary risk of exposure to study participants.

\*\* Blood samples will no longer be taken in order to prevent unnecessary risk of exposure to study participants.

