## 9.3 Study Drug Supply

Study drug packs will be packaged and labelled by Victoria Pharmaceuticals, [name]. Study drug packs consist of:

Valaciclovir 500mg capsules in bottles containing 210 capsules

Matched placebo (Avicel®PH) capsules in bottles containing 210 capsules

Study drug packs of valaciclovir 500mg or placebo capsules will be labelled in compliance with the applicable regulatory requirements. Study drug packs will be dispatched to the responsible site pharmacist under the instruction of the CI or designee. The CI or designee will monitor the quantity of study drug packs at site to ensure study drug packs are available to facilitate the supply of study drug to patients at the time of recruitment/randomisation and at subsequent study visits.

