## 9.6 Study Drug Dispensing

When a patient is recruited at visit 1 (baseline) and subsequently at visit 2 (week 4) the clinician will complete a trial prescription form and present this to pharmacy. At visit 1 and 2 (baseline and week 4), patients will receive a four week supply (plus one week overage) of valaciclovir 500mg or placebo capsules

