## 9.9 Study Drug Compliance

Patients will be asked to store the medication according to the manufacturer's instructions as detailed on study drug pack label. Patients will be asked to bring all unused medication and empty bottles to visit 2 and visit 3. Research staff will perform a count and return any unused medication and empty bottles to the site pharmacy. Patients who have taken 80% or more of the expected number of tablets will be considered compliant. Non-compliance should be discussed with the PI to determine the appropriateness of continuing/discontinuing the medication.

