## 4. DEFINITION OF TERMS

Term	Definition
Adverse Event (AE)	Any untoward medical occurrence in a participant to whom a medicinal product has been administered including occurrences which are not necessarily caused by or related to that product.
Adverse Reaction (AR)	Any untoward and unintended response in a participant to an investigational medicinal product, which is related to any dose administered to that participant.
Unexpected Adverse Reaction (UAR)	An adverse reaction the nature and severity of which is not consistent with the Reference Safety Information.
Serious Adverse Event (SAE) Serious Adverse Reaction (SAR)	An adverse event or adverse reaction that:  results in death, is life-threatening, requires hospitalisation or prolongation of existing hospitalisation, results in persistent or significant disability or incapacity, consists of a congenital anomaly or birth defect, or any other important medical event(s) that carries a real, not hypothetical, risk of one of the outcomes above.
Suspected Serious Adverse Reaction (SSAR)	Any adverse reaction that is classed in nature as serious and is consistent with the Reference Safety Information (RSI)
Suspected Unexpected Serious Adverse Reaction (SUSAR)	Any adverse reaction that is classed in nature as serious and is not consistent with the Reference Safety Information
The EBV suppression	The EBV suppression is defined as 90% reduction in the viral load.
Per Protocol	The pre protocol population is defined as patients with overall study drug adherence of at least 70%
Overall Study Drug Adherence	Total number of tablets administered i.e. actual number of capsules taken / expected number of capsules taken
MMEF	Mid Expiratory Flow – MMEF 25-75% (L/s).

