## **Efficacy**

The number of patients experiencing suppression of Epstein-Barr virus in the two groups will be compared using Chi-Square test (or Fisher's exact if appropriate) followed by logistic regression adjusting for baseline FEV1 and other covariates if required. The odds ratio and 95% confidence interval will be reported.

The intention-to-treat basis analysis will use a significance level of  $\leq 0.05$  for the primary outcome. Per-protocol analysis will also be conducted which will involve a comparison of treatment groups that includes patients with overall study drug adherence of at least 70%. Subgroup analyses will be performed on the primary outcome for compliance. In order to assess differences in treatment effects between the subgroups we will report odds ratio and 99% CI from the treatment\*subgroup interaction model. Sensitivity analysis will be performed for the primary efficacy outcome excluding patients with a confirmed diagnosis of COVID-19

Additionally, change in viral load (Quantitative PCR) from baseline to week 8 in the two groups will be compared using independent t-test (or non-parametric alternative). The mean difference and 95% confidence interval will be reported.

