  - Change in FEV1/FVC ratio from baseline to week 8, mean(SD) by treatment arm, difference in mean with 95% CI
    - Exploratory Subgroup Analysis\*: EBV Suppression (as defined by 90% reduction in viral load) (Yes, No), mean(SD) by treatment arm, difference in mean and interaction term from ancova with 99% CI
  - Change in MMEF from baseline to week 8, mean(SD) by treatment arm, difference in mean with 95% CI
    - Exploratory Subgroup Analysis\*: EBV Suppression (as defined by 90% reduction in viral load) (Yes, No), mean(SD) by treatment arm, difference in mean and interaction term from ancova with 99% CI
  - Change in PEF from baseline to week 8, mean (SD) by treatment arm, difference in mean with 95% CI
    - Exploratory Subgroup Analysis\*: EBV Suppression (as defined by 90% reduction in viral load) (Yes, No), mean(SD) by treatment arm, difference in mean and interaction term from ancova with 99% CI
  - Exploratory Subgroup Analysis\*: EBV Suppression (as defined by 90% reduction in viral load) (Yes, No), mean(SD) by treatment arm, difference in mean and interaction term from ancova with 99% CI
  - Change in TLCO from baseline to week 8, mean(SD) by treatment arm, difference in mean with 95% CI

- Exploratory Subgroup Analysis\*: EBV Suppression (as defined by 90% reduction in viral load) (Yes, No), mean(SD) by treatment arm, difference in mean and interaction term from ancova with 99% CI
  - Descriptive statistics for lung function including; FEV1, FEV1 as a percentage of the predicted FEV1 value, FVC, FEV1/FVC Ratio, MMEF, PEF and TLCO at baseline, week 4 and week 8, mean(SD) or median (IQR) by treatment arm.
  - Difference between lung function measures at baseline and week 8 in the active and placebo groups separately for all lung function outcomes, mean (SD) within each treatment arm, mean difference and 95% CI
- Participant compliance measured by total number of tablets administered as a proportion of total number of tablets supplied, mean(SD) by treatment arm, mean difference and 95% CI
- **Exploratory Outcomes**
  - Clinical
    - Symptoms measured by CAT score and EQ-5D-5L from baseline to week 8, n(%) by treatment arm, mean difference and 95% CI
      - Descriptive statistics will also be presented at baseline, week 4 and week 8, mean(SD), median (IQR) or n(%) by treatment arm.
    - Suppression of Epstein-Barr virus in the sputum of subjects with COPD from baseline to week 4, n(%) by treatment arm, odds ratio and 95% CI\*

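### The secondary compliance outcome divides by capsules supplied, overage included, so a full completer and a patient who stops at four weeks both score 80%; SAP section 4 divides by capsules expected

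*SAP*

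**What the plan says.** The documents use two denominators for what reads as one quantity.

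- **Supplied.** SAP 2.2 defines the secondary outcome as "Participant compliance measured by total number of tablets administered as a proportion of total number of tablets supplied". Protocol 5.3.2 has the same wording. SAP 8.4 carries it into the analysis: "Participant compliance measured by total number of tablets administered as a proportion of total number of tablets supplied, mean(SD) by treatment arm", with a mean difference and 95% CI.
- **Expected.** SAP section 4 defines Overall Study Drug Adherence as "Total number of tablets administered i.e. actual number of capsules taken / expected number of capsules taken". Protocol 9.9 also works from the expected number: "Patients who have taken 80% or more of the expected number of tablets will be considered compliant".

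The per-protocol analysis in SAP 7.1 "includes patients with overall study drug adherence of at least 70" per cent, which is the section 4 term. The subgroup analysis of the primary efficacy outcome (SAP 8.4) uses bands of 80% and over, 60–79% and under 60%, with no denominator given.

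On supply, Protocol 9.3 lists "Valaciclovir 500mg capsules in bottles containing 210 capsules", with placebo bottles of the same size. Under Protocol 9.6, at visit 1 and again at visit 2, "patients will receive a four week supply (plus one week overage"). The regimen in Protocol 9.7 is two capsules three times a day for 8 weeks, and Protocol 9.1 continues treatment until visit 3, at week 8 give or take 7 days.

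**The concern.** Overage is there so that a patient does not run out before a late visit. Nobody is meant to take all of it, so counting it in the denominator marks full adherence as partial. It also makes the score depend on when visit 3 falls and on how many bottles were dispensed.

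The second dependence is the more serious. A patient who stops before visit 2 never receives the second bottle, so the denominator halves along with the numerator. Stopping a drug early is what a tolerability measure should pick up.

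Compliance is the plan's named measure of tolerability (Protocol 4.3, SAP 7.2). With spirometry stopped by the COVID-19 changes, it is also the only secondary outcome still collected from participants followed under the amended schedule. If the subgroup bands were built on the same variable, the fault would reach a subgroup analysis of the primary efficacy outcome.

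**Working it through.** **Inputs.** Capsules per day: 2 × 3 = 6 (Protocol 9.7). Bottle: 210 (Protocol 9.3). Dispensings: two, at visits 1 and 2 (Protocol 9.6). Planned course: 56 days. Visit 3 window: day 49 to day 63 (Protocol 9.1).

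**Reproducing the plan's bottle size.** Four weeks plus one week is 35 days, and 35 × 6 = 210, which agrees exactly. Four weeks alone would be 28 × 6 = 168.

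**Totals.** Supplied = 2 × 210 = 420. Expected over 56 days = 56 × 6 = 336.

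**A patient who takes every dose:**

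| Visit 3 | Taken | Taken / supplied | Taken / fixed 336 | Taken / (6 × actual days) |
|---|---|---|---|---|
| Day 49 | 294 | 294/420 = 70% | 294/336 = 87.5% | 100% |
| Day 56 | 336 | 336/420 = 80% | 336/336 = 100% | 100% |
| Day 63 | 378 | 378/420 = 90% | 378/336 = 112.5% | 100% |

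A fixed 336 therefore removes the overage but keeps the effect of visit timing. Only actual days remove both.

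**A patient who takes every dose for 28 days and stops before the second dispensing.** Taken = 28 × 6 = 168. Taken over supplied = 168/210 = 80%. Taken over the planned course = 168/336 = 50%. On the supplied scale this equals the score of a full 56-day completer.

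**Effect on an arm mean (illustration).** The sample size section plans 44 per arm with 31 evaluable, so 13 are lost. As an extreme assumption, suppose all 13 in one arm stop in this way, the other 31 take everything for 56 days, and nobody in the other arm stops or misses a dose. On the supplied scale both arm means are 80% and the difference is 0. On the planned-course scale the first arm averages (31 × 100 + 13 × 50)/44 = 85.2% against 100%, a difference of 14.8 percentage points.

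**Subgroup bands, if the supplied measure were used for a 56-day patient:**

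| Band edge | Capsules needed, supplied scale | As a share of expected | Capsules needed, expected scale |
|---|---|---|---|
| 80% | 336 | 336/336 = 100% | 269 |
| 60% | 252 | 252/336 = 75% | 202 |

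One missed capsule gives 335/420 = 79.8%, just below the top band, although the patient took 335/336 = 99.7% of expected doses. A patient who misses nothing over 56 days scores exactly 80% and stays in the top band.

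**The case against.** **Section 4 already settles the matter.** It is the SAP's definitions section and it divides by expected, so an analyst might use it everywhere. That protects every analysis that names the section 4 term. It does not protect the secondary outcome, because SAP 2.2 and 8.4 spell out a different formula.

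**The thresholds themselves.** A reader might infer that overage also distorts the per-protocol set and the protocol's 80% rule. The documents do not support this. The 70% cut applies to the section 4 adherence term and the 80% rule refers to the expected number, so neither uses supplied capsules.

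**The bands.** A reader might also take it as settled that the bands misclassify patients. The SAP does not say which measure they use. The shell table for the bands is labelled *Overall Compliance*, as is the shell table for the supplied-based secondary outcome, which points one way. The only defined term is expected-based, which points the other. The misclassification is conditional.

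**A ceiling of 80%.** It is tempting to say the outcome cannot exceed 80%. It can: full adherence to day 63 gives 90%.

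**The differing cut-offs.** The 80% rule labels a patient compliant, with non-compliance then discussed with the investigator; 70% defines an analysis set; the bands define subgroups. These are different uses, and nothing requires the per-protocol cut to fall on a band edge.

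**The comparison between arms.** Among 56-day patients dispensed both bottles, every score is multiplied by 336/420 = 0.8, so the mean difference shrinks by that factor and the t-test p-value is unchanged. This is right for those patients. It fails once some patients stop before the second bottle. Adverse reactions, reasons for stopping and withdrawals are reported elsewhere in the SAP, so early stopping would still be visible there, but not in the outcome named for tolerability.

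**The supply.** Protocol 10.1.2 and 10.1.3 mention only four weeks' supply per visit. If that were all, a full completer would score 336/336 = 100%. The 210-capsule bottle agrees with Protocol 9.6 instead, and the sections should be reconciled.

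**Conclusion.** The inconsistency is real, and the formula as written gives a wrong value for the named tolerability outcome. Full adherence is reported 20 percentage points low at day 56 (80% instead of 100%) and anywhere from 70% to 90% across the permitted visit window. A four-week stopper who took every dose until then is indistinguishable from a full completer, at 80% each, against 50% and 100% of the planned course.

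This rests on both 210-capsule bottles being dispensed to patients who reach visit 2, and on only one being counted as supplied for those who stop before it. Any effect on the subgroup bands depends on a denominator that the SAP leaves unstated. The per-protocol set, the protocol's 80% rule and the intention-to-treat primary analysis are unaffected.

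**What to change.** 1. In Protocol 5.3.2 and SAP 2.2 and 8.4, replace supplied with expected. Use the single section 4 adherence variable for the secondary outcome, the per-protocol set and the bands, and name it in each shell table.
2. Define expected in section 4: 6 × days from first dose to the actual visit 3 date for patients who reach the end of treatment, and the planned 336 for patients who stop early.
3. Limit the SAP 3.4 rule that infers overall compliance from one visit to patients whose other count is missing. Applied to an early stopper with only a visit 2 count, it could return 168/168 = 100% even on the expected scale.
4. State that the 80% and 70% cut-offs serve different purposes, or reconcile them. No particular cut-off follows from this point.

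The cost is wording in the SAP and protocol, with whatever approval Protocol 16.4 requires for the latter. Capsule counts, the study drug start date and visit dates are already collected. The change should be made before unblinding, because choosing a denominator afterwards would be open to the charge that the data guided it.
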